6.4. Treatment of Study Drug Overdose

For this study, accidental or intentional oral ingestion of study drug or excessive application onto the skin (e.g., using a greater quantity, or applying more frequently than instructed) will be considered an overdose. Ingestion of a 30 gram tube of tapinarof cream, 1% would result in an oral dose of 300 mg.

The Sponsor does not recommend specific treatment for an overdose; however, in the event of an overdose, the Investigator (or treating physician) should do the following:

- Contact Medical Monitor to discuss the event;
- In the event of excessive topical application, instruct the subject to wash study drug off of the skin and monitor for application-site AEs;
- Closely monitor the subject for AEs/SAEs and laboratory abnormalities;
- Provide general symptomatic treatment as necessary;
- Document the quantity of the excess dose as well as the duration of the overdosing in the eCRF;
- If the Medical Monitor requests a plasma sample for PK analysis, then a blood sample for PK should be obtained within 2 days from the date of the last dose of study drug.

Decisions regarding dose interruptions or modifications following an overdose will be made by the Investigator in consultation with the Medical Monitor based on the clinical evaluation of the subject.

6.5. Pharmacokinetics

Blood samples for PK analysis of tapinarof cream, 1% will be collected at time points indicated in the Schedule of Assessments (Table 1) and Section 7. The actual date and time of each blood sample collection will be recorded as well as the date and time of the last dose of study drug prior to sample collection. Collection, processing, storage, and shipping procedures are provided in the Laboratory Manual.

Concentrations of tapinarof and tapinarof sulfate (metabolite) will be determined in plasma samples using a validated bioanalytical method. Raw data will be archived at the bioanalytical site. From the plasma concentration-time data on Days 1 and 29, the following primary PK parameters will be determined, if data permit: $AUC_{0-\tau}$, C_{max} , t_{max} , and $t_{1/2}$.

Limited PK sampling will be performed on Day 15.

Once the plasma has been analyzed for tapinarof and tapinarof sulfate (metabolite), any remaining plasma may be analyzed for other metabolites.

7. TIMING OF PROCEDURES AND ASSESSMENTS

This section lists the procedures and assessments to be performed at scheduled time points during the study as outlined in the Schedule of Assessments (Table 1). Information on study procedures and assessments is provided in Section 6.

- Any change in timing or any addition of a time point(s) for any planned study assessment must be documented in a "Note to File," which is approved by the relevant Sponsor study team member and then archived in the study Sponsor and site study files; this will NOT constitute a protocol amendment.
- The IRB/IEC will be informed of any safety issues that require alteration of the safety monitoring scheme or amendment of the ICF.

NOTE: Assessments and procedures should be performed pre-dose on clinic visit days.

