 - elimination half-life $(t_{1/2})$

- Analysis of change from Baseline in QTcF (Δ QTcF) at each post-treatment time point on the sampling day with the higher C_{max} (Day 1 or Day 29)
- Concentration-QTc analysis investigating the relationship between tapinar of plasma concentration and ΔQTcF, if data permit
- Mean change from Baseline to Day 29 in PGA, PASI, and %BSA

Statistical Methods:

Safety and PK data will be presented in tabular and/or graphical format and summarized descriptively.

For cardiodynamic ECG assessments, the primary analysis will be based on by-time point analysis to evaluate the effect of tapinarof cream, 1% on the $\Delta QTcF$ at each post-dosing time point using the Intersection Union Test. The effect of tapinarof on ΔHR , ΔPR , and ΔQRS will also be evaluated using the Intersection Union Test. An analysis of categorical outliers will also be performed for changes in HR, PR, QRS, QTcF, T-wave morphology and U-wave presence. In addition, a potential concentration-QTc analysis will be performed if a sufficient number of PK samples are measurable, i.e., above the lower limit of quantification, to provide a PK profile in most subjects. In this concentration-QTc analysis, the relationship between tapinarof plasma concentrations and $\Delta QTcF$ will be evaluated using a linear mixed-effects modeling approach.

PGA, PASI, and %BSA will be compared to Baseline values using a one sample t-test.

SCHEDULE OF ASSESSMENTS

Table 1: Schedule of Assessments

		Treatment Period (Tapinarof Cream, 1% Once Daily)						Follow-up		
Procedure	Screening (up to 34 days prior to Day 1)	Day -1	Baseline Day 1	Day 2	Day 8	Day 15	Day 22	Day 29	Day 30	(7-10 days after Day 29) or ET
	Visit 1	Visit 2	Visit 3	Visit 4	Phone Call	Visit 5	Phone Call	Visit 6	Visit 7	Visit 8
Informed consent	X									
Inclusion and exclusion criteria	X	X	X							
Demography	X									
Brief physical exam (including height, weight and BMI at Screening)	X									X
Medical history (including year of psoriasis diagnosis)	X									
Pregnancy test (WOCBP)	X		X							X
PGA, PASI, and % BSA evaluation ^a	X		X					X		
HIV, Hep B and Hep C Screen	X									
Laboratory assessments (chemistry including liver chemistries, hematology, urinalysis)	X		X					X		X
LTS assessment by Investigator			X			X		X		
Single 12-lead ECG	X									X
Continuous Holter Monitoring		X ^b	X ^c	X ^d				X ^c	X ^d	
Vital signs (pre-dose; HR, BP, and temperature)	X		X							X
Randomization			X							

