Study drug Dispensation / Collection			X			X		X		
Training on drug application			X	X	X	X	X			
Dispense/collect subject diary			X			X		X		
Tapinarof cream administration in- clinic under site supervision			X	X		X		X		
Serial PK profile samples ^e			X	X		X		X	X	
			X	X				X	X	
AE/SAE review	X	X	X	X	X	X	X	X	X	X
Concomitant medication review	X	X	X	X	X	X	X	X	X	X

Note: Phone calls to subjects are on Day 8 and Day 22

Abbreviations: %BSA = percent body surface area; AE = adverse event; BMI = body mass index; BP = blood pressure; ECG = electrocardiogram; ET = early termination; Hep = hepatitis; HIV = human immunodeficiency virus; LTS = local tolerability scale; PGA = Physician Global Assessment; PASI = Psoriasis Area and Severity Index; PK = pharmacokinetic; SAE = serious adverse event; WOCBP = women of childbearing potential

- ^a The subject's scalp, palms, and soles should be excluded from the %BSA calculations.
- b On Day -1, a Holter monitor will be attached for approximately 13 hours to collect pre-treatment, time-matched ECG data. 12-lead ECGs will be extracted from the continuous recording at time points corresponding to time points on Day 1 and Day 29. Subjects will rest in a supine or semi-recumbent position for at least 10 minutes before and 5 minutes after each time point for ECG extraction.
- ^c On Day 1 and Day 29, a Holter monitor will be attached one hour prior to dosing and for 12 hours post-dose. 12-lead ECGs will be extracted at the same time points as PK samples, i.e., pre-dose and at 1, 2, 3, 4, 5, 8, and 12 hours post-dose. Subjects will rest in a supine or semi-recumbent position for at least 10 minutes before and 5 minutes after each time point for ECG extraction. All ECG extractions will be performed immediately before the PK sample is drawn.
- d On Day 2 and Day 30, a Holter monitor will be attached for one hour prior to the 24-hour post-dose PK time point to allow for extraction of 12-lead ECGs corresponding to the 24-hour post-dose PK time point. Subjects will rest in a supine or semi-recumbent position for at least 10 minutes before and 5 minutes after the time point for ECG extraction. The ECG extraction will be performed immediately before the PK sample is drawn.

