1.3.3. Overall Benefit Risk

Taking into account the measures taken to minimize risk to subjects in this study, the potential risks identified in association with tapinarof are justified by the anticipated benefits that may be afforded to subjects with psoriasis.

OBJECTIVES AND ENDPOINTS 2.

The objectives and associated endpoints of the study are as follows:

Objectives	Associated Endpoint
Primary	Primary
To evaluate the safety and tolerability of topical tapinarof cream, 1% in adult subjects with extensive plaque psoriasis	 Frequency and severity of AEs (local and systemic) Laboratory and biomarker values Vital signs ECGs Mean Local Tolerability Scale scores by visit
To evaluate the PK of topical tapinarof cream, 1% in adult subjects with extensive plaque psoriasis	 Tapinarof and tapinarof sulfate (metabolite) plasma PK parameters on Day 1 and Day 29, if data permit, including: AUC_{0-τ} C_{max} t_{max} t_{1/2}
Secondary	Secondary
To exclude clinically relevant effects of tapinarof cream, 1% on QTcF	 Analysis of ΔQTcF at each post-treatment time point on the sampling day with the higher C_{max} (Day 1 or Day 29) Concentration-QTc analysis investigating the relationship between tapinar of plasma concentration and ΔQTcF, if data permit
To assess the efficacy of tapinar of cream, 1% in adult subjects with extensive plaque psoriasis	 Mean change from Baseline to Day 29 in PGA, PASI, and %BSA
Exploratory	Exploratory

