Study drug application instructions will be reviewed at all post-randomization clinic visits. On clinic visit days, subjects will be instructed/reminded on how to apply study drug (except during the final treatment/end-of-study visits). During the clinic visits, subjects will apply the daily dose of study drug while on-site under the supervision of site personnel, after other assessments have been completed.

Subjects who withdraw from the study before Day 30 will complete an Early Termination Visit. Study duration for subjects who complete this study is approximately 10 weeks in total. Refer to Section 6 for descriptions of study procedures and assessments and Section 7 and the Schedule of Assessments (Table 1) for timing of procedures and assessments.

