8.1.1. Definition of Adverse Events

An AE is any untoward medical occurrence in a subject temporally associated with the use of a study drug, whether considered causally related or not related to the study drug.

An AE can therefore be any unfavorable and unintended sign (including an abnormal laboratory finding), symptom, or disease (new or exacerbated) temporally associated with the use of a study drug.

Events meeting the definition of an AE include:

- Any abnormal laboratory test results (e.g., hematology, clinical chemistry) or other safety assessments (e.g., vital signs measurements), including those that worsen from Baseline, and felt to be clinically significant in the medical and scientific judgment of the Investigator;
- Exacerbation of a chronic or intermittent pre-existing condition (e.g., atopic dermatitis) including either an increase in frequency and/or intensity of the condition;
 - For skin-related AEs, it should be noted whether or not the event is in the area of active application of study drug, and/or if spreading beyond the application site.
- New conditions detected or diagnosed after study drug administration even though it may have been present prior to the start of the study;
- Signs, symptoms, or the clinical sequelae of a suspected interaction;
- Signs, symptoms, or the clinical sequelae of a suspected overdose of either study drug or a concomitant medication (overdose per se will not be reported as an AE/SAE);
- "Lack of efficacy" or "failure of expected pharmacological action" per se will not be reported as an AE or SAE. However, the signs, symptoms, and/or clinical sequelae resulting from lack of efficacy will be reported as AE or SAE if they fulfill the definition of an AE or SAE.
- Evaluation of local tolerability at the site of topical application (e.g., burning/stinging, pruritus, and erythema).

Events that **do not** meet the definition of an AE include:

- Any clinically significant abnormal laboratory findings or other abnormal safety assessments that are associated with the underlying disease, unless judged by the Investigator to be more severe than expected for the subject's condition;
- The disease/disorder being studied or expected progression, signs, or symptoms of the disease/disorder being studied, unless more severe than expected for the subject's condition:
- Medical or surgical procedure (e.g., endoscopy, appendectomy); the condition that leads to the procedure is an AE.

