### **10.7 Local Tolerability Scale**

Local tolerability scale (LTS) overall score for dryness, erythema, and peeling will be summarized using descriptive statistics at Baseline and at Days 15 and 29 as will the number and percent of subjects who apply study drug to the following sensitive areas: face, neck, skin folds, axilla, inframammary, anal crux, and genitalia. If 5 more subjects treat a sensitive area(s) at any time during the treatment period, LTS scores will be summarized at Baseline and Days 15 and 29 for that specific area(s).

In addition, LTS scores will be listed by subject overall and by sensitive area as applicable.

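### After dosing starts the Local Tolerability Scale is scored only before dosing on Days 15 and 29, so mean LTS by visit misses irritation soon after application and irritation that clears or ends treatment before Day 15

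*Protocol*

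**What the plan says.** Protocol Section 2 lists "Mean Local Tolerability Scale scores by visit" as a primary endpoint for the safety and tolerability objective. It stands beside AE frequency and severity (local as well as systemic), laboratory values, vital signs and ECGs.

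The Table 1 row "LTS assessment by Investigator" is marked for Day 1, Day 15 and Day 29, and Sections 7.3, 7.6 and 7.8 agree. The LTS is absent from Day 2 (Section 7.4), Day 30 (Section 7.9) and Follow-up/Early Termination (Section 7.10).

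Two rules fix the order of scoring and dosing. The note in Section 7 reads "Assessments and procedures should be performed pre-dose on clinic visit days". Section 3.1 has subjects apply the daily dose "while on-site under the supervision of site personnel, after other assessments have been completed", and Section 5.1.5 says the same in substance.

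SAP 10.7 follows this schedule: the LTS "will be summarized using descriptive statistics at Baseline and at Days 15 and 29". SAP Section 6 summarizes observed data only, imputes no missing values, and leaves unscheduled visits to the listings.

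Subjects are nevertheless seen soon after dosing. Table 1, footnote c, says that on Days 1 and 29 "a Holter monitor will be attached one hour prior to dosing and for 12 hours post-dose". Footnotes d and e add a 24-hour ECG and PK sample on Days 2 and 30.

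**The concern.** This is a maximal-use study in subjects with at least 20% of body surface involved. Protocol Section 1.3.1.1 names skin irritation as a risk of the product, and Section 8.1.4 makes contact dermatitis an event of special interest. The LTS is the only instrument by which an investigator grades every subject's application sites on one 0-4 scale at fixed times.

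As scheduled, it describes the residual state of the skin about a day after the previous application, in subjects still in the study at two and four weeks. A low mean at Days 15 and 29 could arise in two ways: little irritation occurred, or irritation occurred early and then cleared or removed the subject. The endpoint cannot tell these apart. A subject who stops before Day 15 has no LTS score after baseline, because the Early Termination visit omits it.

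**Working it through.** The plan states no figure to reproduce here; the sample size of about 20 rests on feasibility. The check is a count from Table 1 and Section 7, followed by an illustration on assumed rates.

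**Timing of the scores.** Table 1 labels vital signs as pre-dose but puts no such label on the LTS. The timing comes from the general rules. The Section 7 note cannot apply literally to post-dose PK and Holter recordings, but those have explicit post-dose times and the LTS has none. So the LTS is pre-dose.

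**Applications before each score.** With once-daily dosing from Day 1:
- Day 1 score: 0 applications.
- Day 15 score: Days 1 to 14 = 14 applications.
- Day 29 score: Days 1 to 28 = 28 applications.

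That gives 2 on-treatment scores over 29 applications. Both fall about 24 hours after the preceding morning's dose, and none is scheduled within 12 hours of any dose.

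**In-clinic post-dose PK time points (Table 1, footnote e).**
- Days 1-2: 1, 2, 3, 4, 5, 8, 12 and 24 h = 8.
- Day 15: 2 and 4 h = 2.
- Days 29-30: 1, 2, 3, 4, 5, 8, 12 and 24 h = 8.
- Total 8 + 2 + 8 = 18, of which 0 carry an LTS.

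**Illustration.** Let p be the share of subjects with early irritation that is gone by Day 15. The documents do not give p, so a range is assumed. With N = 20, the chance of at least one such subject is 1 - (1 - p)^20:

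| p (assumed) | expected subjects, 20p | chance of at least one |
|---|---|---|
| 0.05 | 1 | 64% |
| 0.10 | 2 | 88% |
| 0.20 | 4 | 99% |
| 0.30 | 6 | 99.9% |

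If these subjects would have scored s on Day 2 and all others 0, the Day 2 mean would be p × s. With p = 0.20 and s = 2 it is 0.20 × 2 = 0.40. The same subjects add 0 to the Day 15 and Day 29 means once the irritation has cleared. If instead those 4 had stopped, the Day 15 mean would be taken over 20 - 4 = 16 subjects, without them and without imputation.

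**The case against.** A reader might infer that acute and first-two-week irritation never reaches the primary tolerability assessment. The documents do not support that, for three reasons.

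- Local AEs are a primary endpoint for the same objective. Section 8.1.1 counts local tolerability at the application site among AEs, and Table 1 schedules AE review on Days 1, 2, 8, 15, 22, 29 and 30 and at follow-up.
- Irritation that begins in the first two weeks and persists to Day 15 is scored.
- The Day 15 and Day 29 scores do show reactions present about 24 hours after a dose under repeated use.

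A reader might also infer that irritation leading to discontinuation goes unmeasured. That fails too. SAP 10.4 tabulates treatment-emergent AEs that led to stopping study drug, and AEs by highest severity. Section 8.1.4 requires location, duration, size, symptoms and severity for contact dermatitis and folliculitis, and asks for an unscheduled visit, where possible, for significant irritation between visits.

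It is also fair to say that the schedule is internally consistent, so this is a design choice and not an error, and that local reactions were already described in earlier studies, including a 227-subject psoriasis trial.

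The narrower point stands. Section 8.1 prefers open-ended, non-leading questions for finding AEs. An AE receives a severity grade, but only if it is reported, whereas the LTS scores every subject, including those at zero. SAP 10.4 does not summarize the special-interest events separately. No LTS is specified for an unscheduled visit, and data from such a visit would only be listed.

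Practical objections to scoring at 12 hours also carry weight. With morning dosing it falls in the evening. Section 6.3.6 prefers one rater per subject and requires a separate score for sensitive areas. Skin inspection would also have to stay clear of the supine rest from 10 minutes before to 5 minutes after each ECG time point.

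**Conclusion.** The point holds as a limitation of one primary endpoint. Mean LTS by visit has two on-treatment scores, none before 14 scheduled applications and none in the hours after any dose. It misses irritation soon after application and irritation that resolves, or leads to stopping, before Day 15. These cases reach the primary safety data only through AE and special-interest event reporting.

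The counts are exact, given that the general pre-dose rule applies to the LTS. The effect on the mean is unknown: the 0.40 is an illustration on assumed values, and the documents give no frequency for transient early reactions. Section 1.2 says plasma concentrations peak in the first week, but reading this as the period of most skin irritation would be inference. The change is a worthwhile improvement and not a condition for the study's validity.

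**What to change.** 1. Add an LTS score on Day 2 to Table 1 and Section 7.4, after the 24-hour ECG extraction and PK draw and before the Day 2 application. No PGA is scheduled that day, so the rule that the PGA comes first is not affected.
2. Add an LTS score at Early Termination to Table 1 and Section 7.10, so that subjects who stop before Day 15 have an on-treatment or end-of-treatment score. Follow-up and Early Termination share a column in Table 1, so a footnote can limit the score to Early Termination.
3. Add both time points to SAP 10.7 and Table 14.3.5.2.1, with Early Termination as its own row and not pooled with Day 15 or Day 29.
4. Optional: scores at the 12-hour contacts on Days 1 and 29, after the ECG and PK time point and by the same rater where possible. Day 30 is not needed; it would be another score about 24 hours after a dose, one day after the Day 29 score.

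A completer would then have 3 on-treatment scores in place of 2 (5 with the optional ones). A subject who stops between Days 3 and 14 and attends Early Termination would have 2 post-baseline scores in place of 0.

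The cost is a few minutes of rater time at existing visits. Section 7 allows a time point for a planned assessment to be added by an approved Note to File without a protocol amendment. Days 3 to 14 would still have no scheduled LTS for subjects who continue, and would rely on AE reporting; the study report should say so.

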7.1. Visit 1; Screening Period (Up to 34 Days Prior to Day 1)

After the subject has signed the ICF, potential study subjects will undergo Screening procedures and assessments to confirm eligibility to participate in the study. Screening assessments will include the following:

- Serum pregnancy test (WOCBP only)
- ECG recording
- Medical history recording
- Demography recording
- Brief physical exam (including weight, height, and body mass index [BMI])
- Vital signs measurements
- PGA score
- %BSA affected calculation (performed before PASI); subject's scalp, palms, and soles should be excluded from the %BSA calculations used to determine eligibility
- PASI
- Blood and urine sample collection for clinical laboratory tests (serum chemistry, hematology, diagnostic tests)
- AE recording (from the time the ICF is signed)
- Concomitant medication recording (from the time ICF is signed)

To determine subject eligibility at Screening, a single repeat of tests or procedures may be allowed at the discretion of the Investigator in consultation with the Medical Monitor.

7.2. Visit 2; Day -1

On Day -1, subjects will be reassessed to confirm continued eligibility to participate in the study.

The following additional procedures and assessments will be performed at Visit 2:

- AE recording
- Concomitant medication recording
- Continuous Holter Monitoring for 13 hours

7.3. Visit 3; Day 1 (Baseline)

On Day 1, subjects will be reassessed to confirm eligibility to participate in the study. All subjects who continue to meet study eligibility criteria will receive study drug.

The following additional procedures and assessments will be performed at Visit 3:

- Urine pregnancy test (WOCBP only)
- Vital signs measurements
- PGA score
- %BSA affected calculation (performed before PASI); subject's scalp, palms, and soles should be excluded from the %BSA calculations
- PASI
- Continuous Holter Monitoring for 13 hours (1 hour prior to dosing and 12 hours post-dose)
- Blood and urine sample collection for clinical laboratory tests
- Blood sample collection for PK analysis and
- AE recording
- Concomitant medication recording
- Paper diary dispensed (subjects will be instructed in how and when to complete diary)
- LTS scoring
- Dispense study drug
- Instruction on how to administer study drug
- Study drug administration under supervision

7.4. Visit 4; Day 2

The following procedures and assessments will be performed at Visit 4:

- Continuous Holter Monitoring for 1 hour (1 hour prior to PK sample collection)
- Blood sample collection for PK analysis and
- AE recording
- Concomitant medication recording
- Instruction on how to administer study drug
- Study drug administration under supervision

